10.3.5 Duration of Overall Response and/or Progression-Free Survival (in Non-Responders)

- The duration of overall response is measured from the time measurement criteria are met for CR/PR (whichever is first recorded) until the first date that recurrent or progressive disease is objectively documented (taking as reference for progressive disease the smallest measurements recorded since the treatment started).
- The duration of overall complete response is measured from the time measurement criteria are first met for CR until the first date that recurrent disease is objectively documented.
- Duration of Stable Disease

- Stable disease is measured from the start of the treatment until the criteria for progression are met, taking as reference the smallest measurements recorded since the treatment started.

10.4 Duration of Overall Survival

Duration of Overall Survival is measured from the start of treatment until death for any reason (cause of death will be documented whenever possible). Patients that progress at any time will be followed for survival only, on a yearly basis either by review of medical records or a phone call.

11 SAFETY EVALUATION

11.1 Adverse Events

11.1.1 Definition

An adverse event or adverse experience (AE) is any untoward medical occurrence associated with the use of a drug in humans, whether or not considered drug related. Therefore, an AE can be ANY unfavorable and unintended sign (including an abnormal laboratory finding), symptom, or disease temporally associated with the use of a medicinal (investigational) product, whether or not considered related to the medicinal (investigational) product (attribution of ‘unrelated’, ‘unlikely’, ‘possible’, ‘probable’, or ‘definite’).

An AE is considered “unexpected” if it is not listed in the investigator brochure or is not listed at the specificity or severity that has been observed; or if an investigator brochure is not required or available, is not consistent with the risk information described in the general investigational plan in other study-related documents.

11.1.1.1 Diagnosis Versus Signs and Symptoms

If known, a diagnosis should be recorded on the CRF rather than individual signs and symptoms (e.g., record only liver failure or hepatitis rather than jaundice, asterixis, and elevated transaminases). However, if a constellation of signs and/or symptoms cannot be clinically characterized as a single diagnosis or syndrome at the time of reporting, each individual event should be recorded as an AE or SAE on the CRF. If a diagnosis is subsequently established, it should be reported as follow-up information.

11.1.1.2 Adverse Events Occurring Secondary to Other Events

In general, AEs occurring secondary to other events (e.g., cascade events or clinical sequelae) should be identified by their primary cause. For example, if severe diarrhea is known to have resulted in dehydration, it is sufficient to record only diarrhea as an AE or SAE on the CRF.

However, clinically significant AEs occurring secondary to an initiating event that are separated in time should be recorded as independent events on the CRF. For example, if a severe gastrointestinal hemorrhage leads to renal failure, both events should be recorded separately on the CRF.

11.1.1.3 Abnormal Laboratory Values

Only clinically significant laboratory abnormalities that require active management will be recorded as AEs or SAEs on the CRF (e.g., abnormalities that require study drug dose modification, discontinuation of study treatment, more frequent follow-up assessments, further diagnostic investigation, etc.).

If the clinically significant laboratory abnormality is a sign of a disease or syndrome (e.g., alkaline phosphatase and bilirubin 5 x the upper limit of normal associated with cholecystitis), only the diagnosis (e.g., cholecystitis) needs to be recorded on the Adverse Event CRF.

If the clinically significant laboratory abnormality is not a sign of a disease or syndrome, the abnormality itself should be recorded as an AE or SAE on the CRF. If the laboratory abnormality can be characterized by a precise clinical term, the clinical term should be recorded as the AE or SAE. For example, an elevated serum potassium level of 7 mEq/L should be recorded as “hyperkalemia”

Observations of the same clinically significant laboratory abnormality from visit to visit should not be repeatedly recorded as AEs or SAEs on the CRF, unless their severity, seriousness, or etiology changes.

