3. OBJECTIVES

3.1. Phase I Primary Objectives

- To estimate the maximum tolerated dose (MTD) and examine the dose-limiting toxicities of carfilzomib when administered in combination with rituximab, ifosfamide, carboplatin, and etoposide (C-R-ICE) in patients with relapsed/refractory DLBCL.
- To assess the toxicity of dose regimen using the CTEP NCI Common Terminology Criteria for Adverse Events (CTCAE Version 4.0).

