7.4. Dose Modifications

7.4.1. Definition of Dose-Limiting Toxicity

For this protocol, a DLT will be defined by the occurrence of the following toxicity, related to study drug, within cycle 1 of treatment. Patients that experience a DLT will be continued on treatment, per PI discretion, at one level of dose reduction.

- Any \geq Grade 3 non-hematologic adverse event attributed (definitely, probably, or possibly) during C-R-ICE therapy and meeting the following criteria and for hematologic toxicity see **Section 0**.

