7.4.1.1 Non-Hematologic Toxicity

For non-hematologic toxicities, DLT will be defined as any CTCAE v4.0 Grade 3 or greater toxicity, except for:

- Grade 3 or Grade 4 nausea and vomiting lasting less than 72 hours after the last dose of chemotherapy with use of standard anti-emetic therapy.
- Grade 3 non-hematologic laboratory abnormalities that resolve to Grade 1 or baseline (if the patient entered the study with existing toxicity) within 14 days.
- In the event that Grade 3 or Grade 4 adverse events are obviously unrelated to study drug and thus not DLT, the principal investigator will determine whether dose escalation or cohort expansion is required.

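### Section 11.1.1.3 keeps Grade 3-4 laboratory values off the AE form unless they are judged significant and actively managed, so AE-form rates of laboratory toxicity, mainly cytopenias, may be too low

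*Combined protocol and SAP*

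**What the plan says.** **Recording rule.** Section 11.1.1.3 states: "Only clinically significant laboratory abnormalities that require active management will be recorded as AEs or SAEs on the CRF". Its examples of active management are wide and open-ended: "abnormalities that require study drug dose modification, discontinuation of study treatment, more frequent follow-up assessments, further diagnostic investigation, etc". The rule makes no exception by CTCAE grade.

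**AE definition and reporting tables.** Section 11.1.1 is broader: "an AE can be ANY unfavorable and unintended sign (including an abnormal laboratory finding". In Section 11.1.3, Table 4 asks for every grade and every attribution in Phase I. Table 5 asks for Grades 3 and 4 at every attribution in Phase Ib.

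**DLT rule.** Section 7.4.1 builds the non-hematologic DLT on a Grade 3 or higher "non-hematologic adverse event attributed (definitely, probably, or possibly) during C-R-ICE therapy". Section 7.4.1.1 adds that "DLT will be defined as any CTCAE v4.0 Grade 3 or greater toxicity, except for" a short list. The laboratory exception in that list is "Grade 3 non-hematologic laboratory abnormalities that resolve to Grade 1 or baseline (if the patient entered the study with existing toxicity) within 14 days". Section 7.4.1.2 defines the hematologic DLT as a dose delay of more than two weeks, not by grade.

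**Objectives and analysis.** A Phase I primary objective (Section 3.1) is "To assess the toxicity of dose regimen using the CTEP NCI Common Terminology Criteria for Adverse Events". Safety is a primary objective of Phase Ib (Section 3.2). Section 13.5.3 estimates toxicity rates as simple relative frequencies with Clopper-Pearson intervals and does not name the data source.

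**The concern.** Two rules decide what counts as laboratory toxicity, and they use different tests. The DLT definition and the CTCAE objective use grade. The AE form uses the investigator's view of clinical significance and of the need for management. A Grade 3-4 result can pass the first test and fail the second.

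At stake are the toxicity rates that serve a primary objective in each phase. If they are tabulated from the AE form, they can only miss laboratory events, never add them, and the shortfall will vary with who is recording. A secondary question is whether a laboratory DLT could be missed in a dose-finding scheme that turns on one or two events in six patients.

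**Working it through.** The plan states no figure that depends on laboratory AE recording: no DLT rate, no operating characteristics for the 3+3 scheme, and no share of events recorded. There is nothing to reproduce, so the check sets the sections side by side and then adds a sensitivity calculation.

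**1. Cytopenias.**
- Section 7.4.2.3 says doses are usually not adjusted for hematologic toxicity and that the next cycle waits for count recovery.
- Table 3, footnote 8, schedules blood counts three times a week between cycles for everyone. Section 8.3.1 gives growth-factor support on Day 8 to everyone.
- Section 7.4.2 has a carfilzomib hold for ANC below 500/mm³, but a hold matters only if a dose is due.
- A Grade 3-4 nadir between doses that recovers before the next cycle therefore need not trigger a dose change, extra follow-up or work-up. Under Section 11.1.1.3 it can stay off the AE form, although it is a CTCAE Grade 3-4 toxicity.

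**2. DLTs.** Most DLT-level laboratory events already meet the recording rule or are not DLTs:
- A hematologic DLT is itself a dose delay.
- Grade 3 chemistry that resolves within 14 days is exempt.
- A liver abnormality of Grade 3 or higher leads to a hold (Section 7.4.2.7).
- Creatinine clearance below 30 mL/min leads to a hold (Sections 7.3 and 8.1).
- Tumor-lysis-type changes before dosing mean no dose and re-evaluation within 24 hours (Section 8.2).

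What remains is an attributed Grade 4 non-hematologic value, or a Grade 3 value not resolved within 14 days, that led to no hold, re-test or work-up.

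**3. Data source.** Table 3 schedules chemistry on Days 1, 2, 8 and 9 as well as the blood counts. No section says that CTCAE grades or DLTs will be derived from these results.

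**4. Sensitivity of the dose decision.** Table 2 accepts a dose at no more than 1 DLT in 6. Let p be the true DLT probability and c the share of DLTs captured; both are assumptions. The chance that the dose passes is

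P = (1 − pc)⁶ + 6·pc·(1 − pc)⁵.

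- p = 0.33, c = 1: 0.67⁶ + 6 × 0.33 × 0.67⁵ = 0.0905 + 0.2673 = 35.8%.
- p = 0.33, c = 0.95 (pc = 0.3135): 0.1047 + 0.2868 = 39.1%.
- p = 0.33, c = 0.80 (pc = 0.264): 0.1590 + 0.3421 = 50.1%.
- p = 0.20, c = 1, 0.9 and 0.8: 65.5%, 70.4% and 75.3%.

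For a single missed event, 2/6 (33%, 95% CI 4.3% to 77.7%; fails) is read as 1/6 (17%, 95% CI 0.4% to 64.1%; passes). Given step 2, c for DLTs may be close to 1, where the effect is small.

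**The case against.** The strongest reply has four parts.

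- **Active management is broad.** An unscheduled repeat test is enough to put a value on the form. The section's own example, a potassium of 7 mEq/L recorded as hyperkalemia, mentions no treatment. This stands, and it shrinks the chemistry gap. It does not cover a nadir seen on counts that every patient has anyway, and clinical significance remains a separate judgment.
- **The rule governs the CRF, not the definition of an AE.** A Grade 4 value is still an AE under Section 11.1.1, and nothing says DLTs are counted from the AE form alone. Table 3 has a separate drug toxicity assessment, and Section 12 has Phase I studies reviewed at scheduled meetings. This also stands: a DLT kept off the form is not necessarily a DLT missed. But neither provision says that laboratory results are graded.
- **The DLT gap is narrow.** Agreed, for the reasons in step 2 of the working.
- **The dose-decision arithmetic is generic.** Any missed DLT moves 2/6 to 1/6, and the decision reverses only if the recorded count is exactly 1 and the true count is higher. Agreed; it shows sensitivity, not an effect in this trial.

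A reader might infer that the safety of Dose Level 6 has been overstated. The documents do not support that. Section 4.1 names the level as the Phase Ib dose but gives no DLT count, laboratory grade or capture rate for it.

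**Conclusion.** The inconsistency is real and should be corrected. Section 11.1.1.3, read as written, conflicts with Section 11.1.1, Table 4 and the grade-based rule in Section 7.4.1.1. The main consequence is a possible downward, investigator-dependent bias in AE-form rates of Grade 3-4 laboratory toxicity, chiefly uncomplicated cytopenias. This assumes that the rates in Section 13.5.3 are tabulated from the AE form, which the plan neither states nor rules out. The size of the bias cannot be estimated, because the documents give neither the frequency of Grade 3-4 cytopenia nor the share needing management.

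The consequence for DLTs is secondary: an unmanaged Grade 4, or persistent Grade 3, non-hematologic value could be missed. Whether one was missed at Dose Level 6 cannot be known from the documents, so the right response is a check.

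**What to change.** 1. State in Sections 11.1.1.3 and 13.5.3 that laboratory toxicity rates use the worst CTCAE v4.0 grade per patient per cycle, derived from the scheduled blood count and chemistry results. Alternatively, require that every Grade 3 or higher laboratory value be recorded whether or not it was managed.
2. State that Section 7.4.1.1 is applied to those grades, with attribution assessed as now, and that Section 11.1.1.3 governs narrative AE reporting only.
3. Say how a Grade 3 chemistry value on Day 9 with no repeat is classified. Scheduled chemistry ends at Day 9 and the next cycle starts no sooner than Day 22 (Section 7.3), a gap of at least 22 − 9 = 13 days, so the 14-day resolution test may rest on a single later result.
4. Check the Cycle 1 DLT count for the Phase I patients at Dose Level 6 once against their laboratory results, and report the outcome either way.

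**Cost.** No new visits or samples. Some data entry or programming is needed if results are not already held electronically; Section 16.1 does not confirm that every result enters the database. Section 14.2 models the time course of thrombocytopenia and neutropenia, so counts will have to be assembled for at least the patients in that model. Reported Grade 3-4 laboratory rates will probably be higher, which the report should explain as a change in data source.

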11.1.1.4 Preexisting Medical Conditions (Baseline Signs and Symptoms)

A preexisting medical condition should be recorded as an AE or SAE only if the frequency, severity, or character of the condition worsens during the study. When recording such events on an Adverse Event CRF, it is important to convey the concept that the preexisting condition has changed by including applicable descriptors (e.g., “more frequent headaches”).

11.1.2 Grading and Relationship to Drug

The descriptions and grading scales found in the CTEP Version 4 of the NCI Common Terminology Criteria for Adverse Events (CTCAE) will be utilized for AE reporting. CTEP Version 4 of the CTCAE is identified and located at: http://ctep.cancer.gov/protocolDevelopment/electronic_applications/ctc.htm. AEs not covered by specific criteria should be reported with common medical terminology and graded according to definitions provided in the CTCAE Version 4.

The relationship of event to study drug will be documented by the Investigator as follows:

- **Unrelated:** The event is clearly related to other factors such as the patient's clinical state, other therapeutic interventions or concomitant drugs administered to the patient.
- **Unlikely:** The event is doubtfully related to investigational agent(s). The event was most likely related to other factors such as the patient's clinical state, other therapeutic interventions, or concomitant drugs.
- **Possible:** The event follows a reasonable temporal sequence from the time of drug administration, but could have been produced by other factors such as the patient's clinical state, other therapeutic interventions or concomitant drugs.

- **Probable:** The event follows a reasonable temporal sequence from the time of drug administration, and follows a known response pattern to the study drug. The event cannot be reasonably explained by other factors such as the patient's clinical state, therapeutic interventions or concomitant drugs.
- **Definite:** The event follows a reasonable temporal sequence from the time of drug administration, follows a known response pattern to the study drug, cannot be reasonably explained by other factors such as the patient's condition, therapeutic interventions or concomitant drugs; AND occurs immediately following study drug administration, improves upon stopping the drug, or reappears on re-exposure.

11.1.3 Reporting Adverse Events

Table 4. Guidelines for Routine Adverse Event Reporting for Phase I Studies (Regardless of Expectedness)

Attribution	Grade 1	Grade 2	Grade 3	Grade 4
Unrelated	X	X	X	X
Unlikely	X	X	X	X
Possible	X	X	X	X
Probable	X	X	X	X
Definite	X	X	X	X

Table 5. Guidelines for Routine Adverse Event Reporting for Phase Ib Studies (Regardless of Expectedness)

Attribution	Grade 1	Grade 2	Grade 3	Grade 4
Unrelated			X	X
Unlikely			X	X
Possible	X	X	X	X
Probable	X	X	X	X
Definite	X	X	X	X

All new routine AEs occurring between the start date of intervention until 30 days after the last intervention or until the event has resolved, stabilized, death, or a new treatment is started, whichever comes first, will be reported.

11.2 Serious Adverse Events

11.2.1 Definition

A serious adverse event (SAE) is any adverse event (experience) that in the opinion of either the investigator or sponsor results in **ANY** of the following:

- Death.

- A life-threatening adverse event (experience). Any AE that places a patient or patient, in the view of the Investigator or sponsor, at immediate risk of death from the reaction as it occurred. It does NOT include an AE that, had it occurred in a more severe form, might have caused death.
- Inpatient hospitalization or prolongation of existing hospitalization (for > 24 hours).
- A persistent or significant incapacity or substantial disruption of the ability to conduct normal life functions.
- A congenital anomaly or birth defect.
- Important Medical Event (IME) that, based upon medical judgment, may jeopardize the patient or patient and may require medical or surgical intervention to prevent one of the outcomes listed above.

11.2.2 Reporting Serious Adverse Events

All new SAEs occurring from the date the patient signs the study consent until 30 days after the last intervention or a new treatment is started, whichever comes first, will be reported. SAE's occurring after this time that the investigator determines to be possibly, probably or definitely related to the study intervention, should be reported.

The Roswell Park SAE Source Form is to be completed with all available information, including a brief narrative describing the SAE and any other relevant information. The site Investigator or designated research personnel will report all SAEs, whether related or unrelated, to the investigational agent(s) to the IRB in accordance with their local institutional guidelines.

SAE's identified as an Unanticipated Problem by the Investigator must be reported. Please refer to Section 11.5 for details on reporting Unanticipated Problems.

Amgen should receive copies of all safety reports submitted to the FDA, or any regulatory agency, IRB or IEC, within 24 hours of such submission. Such notifications should be submitted as MedWatch reports using the attached SAE fax cover letter and faxed to [name]. Note the fax cover must contain both Amgen and Onyx study numbers, as reflected in the attached form (Appendix D).

11.3 Investigator Reporting: Notifying the Study Sponsor

Notify the study sponsor: SAEs should be reported to Amgen by fax to: **[contact]**.

11.4 Follow-Up for Serious Adverse Events

All SAEs will be followed until resolution, stabilization, death, or the start of new treatment. New information will be reported when it is received.

11.5 Unanticipated Problems

11.5.1 Definition

An Unanticipated Problem (UP) is any incident, experience, or outcome that meets all of the following criteria:

- Unexpected (in terms of nature, severity, or frequency) given:
 - a) The research procedures that are described in the study-related documents, including study deviations, as well as issues related to compromise of patient privacy or confidentiality of data.
 - b) The characteristics of the patient population being studied.
- Related or possibly related to participation in the research (possibly related means there is a reasonable possibility that the incident, experience, or outcome may have been caused by the procedures involved in the research).
- Suggests that the research places patients or others at a greater risk of harm (including physical, psychological, economic, or social harm) than was previously known or recognized and if in relation to an AE is also deemed Serious per **Section 11.2**.

11.5.2 Reporting Unanticipated Problems

The Unanticipated Problem Form will be submitted to CRS Compliance Office within 1 business day of becoming aware of the Unanticipated Problem.

When becoming aware of new information about the Unanticipated Problem, submit this updated information to CRS Compliance with an updated Unanticipated Problem Form. The site Investigator or designated research personnel will report all unanticipated problems, whether related or unrelated to the investigational agent(s) to the **IRB in accordance with their local institutional guidelines**.

11.6 FDA Reporting

When Roswell Park is the IND holder the following describes the FDA reporting requirements by timeline for AEs and new safety findings that meet the criteria outlined below:

Within 7 Calendar Days

Any adverse event that meets **ALL** the following criteria:

Related or possibly related to the use of the study drug;

Unexpected; and Fatal or life-threatening.

Within 15 Calendar Days

Any adverse event that meets **ALL** the following criteria:

Related or possibly related to the use of the study drug;

Unexpected; and Serious but not fatal or life-threatening.

Or meets **ANY** of the following criteria:

A previous adverse event that is not initially deemed reportable but is later found to fit the criteria for reporting (report within 15 days from when event was deemed reportable).

Any findings from other studies, including epidemiological studies, pooled analysis of multiple studies, or other clinical studies conducted with the study drug that suggest a significant risk in humans exposed to the drug.

Any findings from animal or in vitro testing that suggest a significant risk for human patients including reports of mutagenicity, teratogenicity, or carcinogenicity or reports of significant organ toxicity at or near the expected human exposure.

Any clinically important increase in the rate of occurrence of a serious, related or possibly related adverse event over that listed in the protocol or investigator brochure.

Sponsors are also required to identify in IND safety reports, all previous reports concerning similar adverse events and to analyze the significance of the current event in the light of the previous reports.

Reporting Process

The principal investigator or designee will complete and submit a FDA Form 3500A MedWatch for any event that meets the above criteria. Forms will be submitted to the CRS Compliance Office via email to: [contact].

